### **Sample Size Calculation**

The required sample size was calculated using G\*Power software. Based on repeated measures analysis of variance, the sample size for each group was at least 27 (effect size = 0.25,  $\alpha$  = 0.05, power = 0.95). To avoid the impact caused by loss, an additional 10 people were included in each group, that is, 37 people. A total of 74 people

were recruited in two groups.

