### **Data preparation and statistical analysis**

Before formal analysis, this study addressed errors and outliers in the three tasks, respectively. Trials with incorrect reactions and with RTs greater than 3000ms, lower than 200ms, or greater than  $\pm 3$  standard deviation were excluded when calculating each participants' task performances. We also treated attention, interpretation and memory bias index of  $\pm 3$  standard deviation as extreme values.

Firstly, group differences across these two groups were measured using t-tests for scale and behavioral variables, and Chi-square tests for sociodemographic variables. To explore the intervention effect of tDCS on task performance, repeated-measures ANOVA were conducted with "group" (tDCS vs. sham group) as the between-subject and "time" (pre-test vs. post-test) as the within-subject factors. The outcomes of dot probe task, word sentence association paradigm and free recall and recognition task served as dependent variables. Before the ANOVA analysis, we used the Levene test to evaluate the homogeneity of variance of the data and the results showed that the data basically satisfied the homogeneity of variance hypothesis. The Bartlett and Mauchly's test were also performed to assess the sphericity of the data, and the degrees of freedom were modified by the Greenhouse-Geisser approach if needed. For subjective scale data, we employed 2-level linear mixed-effects regression, which included three fixed effects (group, time and the interaction between group and time) and one random effect (participants). All of these analyses were conducted using SPSS 25.0 and R software. The significance level was set at  $p < 0.05$ , and the marginal significance level was set at  $p < 0.1$ . Effect sizes were reported by the partial eta-squared ( $\eta^2$ ) for ANOVA, and the Cohen's d for pairwise comparisons.

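### Task outcomes are tested as unadjusted change in participants with both visits; a baseline-constrained mixed model on everyone randomised would be more precise at almost no cost

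*Combined protocol and SAP*

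**What the plan says.** All references are to the combined protocol and SAP.

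- **Task model** (Data preparation and statistical analysis). "To explore the intervention effect of tDCS on task performance, repeated-measures ANOVA were conducted with" group as the between-subject factor. The time factor has two levels: "pre-test vs. post-test) as the within-subject factors". It covers every task measure: "The outcomes of dot probe task, word sentence association paradigm and free recall and recognition task served as dependent variables".
- **Questionnaire model** (same section). "For subjective scale data, we employed 2-level linear mixed-effects regression", with group, time and their interaction as fixed effects and one random effect for participant.
- **Loss** (Sample Size Calculation). At least 27 per group are required; to guard against loss, "an additional 10 people were included in each group", giving 37 per group and 74 in total.
- **Visits** (Interventions and study procedures). The tasks are done before the first and after the last stimulation of a 5-day course. The 4-week follow-up covers psychological symptoms only.
- **Outliers** (Data preparation and statistical analysis). Trials that are wrong or have outlying response times "were excluded when calculating each participants' task performances". For participant-level scores the text is: "We also treated attention, interpretation and memory bias index of" ±3 "standard deviation as extreme values". It does not say whether such a score is removed, replaced or kept, or over which group and visit the SD is taken.

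No section defines an analysis population, the handling of a missing post-test, or a sensitivity analysis.

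**The concern.** The aim at the end of the Literature review puts cognitive bias first and social anxiety symptoms second. The tasks are the behavioural measure of cognitive bias, yet they receive the less efficient analysis.

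A two-level within-subject ANOVA needs both values, so a randomised participant without a post-test drops out. The plan does not state this; it follows from the method when nothing is imputed. With two visits, the group-by-time F test is also the same as a t test on change scores. Baseline is then simply subtracted, which is inefficient unless the pre-post correlation is close to 1.

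Two things are at stake: precision, and protection of the randomised comparison if loss depends on baseline differently in the two arms. The silence on ±3 SD scores adds a third, because removal would exclude randomised participants on the value of their own outcome, with a possibly different subset for each measure.

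**Working it through.** **1. The plan's own figure.** Inputs from Sample Size Calculation: effect size 0.25 (taken as Cohen's f), alpha 0.05, power 0.95. Assumed, because not stated: pre-post correlation r = 0.5, and the within-between interaction with two groups and two visits.

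λ = f² × N × m / (1 − r) = 0.0625 × 54 × 2 / 0.5 = 13.5, with 1 and 52 degrees of freedom. Power is 95.0% at N = 54, so 27 per group reproduces. The margin is 10/37 = 27.0% per arm. Power is 98.9% if all 74 are analysed.

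**2. Variance per arm** of the estimated effect, in units of the single-visit variance, with n completers of N randomised per arm:

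- ANOVA on completers (change): 2(1 − r)/n
- Mixed model, separate baseline means: (1 − r²)/n + (1 − r)²/N
- Mixed model, common baseline mean: about (1 − r²)/n

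At n = 27, N = 37, r = 0.5 these are:

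- 1/27 = 0.0370
- 0.75/27 + 0.25/37 = 0.0345
- 0.75/27 = 0.0278

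**3. Reductions relative to the ANOVA.**

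- From keeping incomplete participants only: [(1 − r)/2] × (1 − n/N)
- From the common baseline: 1 − (1 − r²)/[2(1 − r)] = (1 − r)/2, in which n and N cancel

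| r (assumed) | Keeping incomplete, 27 of 37 complete | Common baseline mean |
|---|---|---|
| 0.3 | 0.35 × 10/37 = 9.5% | 35% |
| 0.5 | 0.25 × 10/37 = 6.8% | 25% |
| 0.7 | 0.15 × 10/37 = 4.1% | 15% |

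With smaller loss at r = 0.5, the middle column becomes 0.25 × 4/37 = 2.7% (33 of 37 complete) or 0.25 × 2/37 = 1.4% (35 of 37). The right-hand column does not change. The two columns are alternatives and must not be added: N does not appear in the common-baseline variance.

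In terms of sample size at r = 0.5, 27 completers per arm with baseline adjustment carry the information of 27/0.75 = 36 analysed by change.

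**4. Bias from baseline-dependent loss, an assumed scenario.** One arm loses 45% above and 9% below the median baseline (27% overall); the other loses 27% at random. For a normal baseline, the mean of each half is ±√(2/π) = ±0.798 SD. The retained mean in the first arm is 0.798 × (0.55 − 0.91)/(0.55 + 0.91) = −0.197 SD. Bias in change is (r − 1) × (−0.197):

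- r = 0.3: 0.14 SD
- r = 0.5: 0.10 SD
- r = 0.7: 0.06 SD

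The same five-fold ratio at 10% overall loss (16.7% and 3.3%) gives a retained mean of 0.798 × (0.833 − 0.967)/1.8 = −0.059 SD, and so a bias of about 0.03 SD at r = 0.5. For scale, f = 0.25 in this design is a difference in change of 4 × 0.25 = 1.0 SD, and the ANOVA standard error with 27 per arm is √(2/27) = 0.27 SD.

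**5. How many scores ±3 SD would flag.** Under normality 0.27% of values, so 148 × 0.0027 = 0.4 of 74 participants per measure over two visits. For a right-skewed measure such as Peak TL-BS, simulation with an assumed log-normal spread of 0.1 to 0.4 between persons flags about 0.8% to 1.4% per visit, or 148 × 0.008 = 1.2 to 148 × 0.014 = 2.1. These are counts flagged. Whether anyone is removed is not stated.

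**The case against.** Several stronger readings are tempting, and the documents do not support them.

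- **That the plan expects 27% of task data to be missing.** It gives no expected rate. Ten per arm is a margin for the whole study, and the tasks span only 5 days. Figures at 27 of 37 are therefore an upper bound.
- **That the 25% gain is the price of losing participants.** It is not: the same gain appears with no loss at all. It measures baseline adjustment against change.
- **That the questionnaire model only needs extending to the tasks.** That model has separate baseline means and a random intercept. With complete data at two visits it gives the same group-by-time test as the ANOVA, so the proposal here is a different model.
- **That participants beyond ±3 SD are removed.** In that paragraph exclusion is stated for trials; for indices the handling is open. Endorsement and accuracy percentages are bounded, so the skewed example does not speak for them.
- **That the task result is known to be biased.** Nothing in the documents suggests differential loss, and the scenario in the working is strong by construction. Even so, it gives about a tenth of the planned effect.

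It is also fair that a mixed model repairs only loss explained by observed data. Loss that depends on the unseen post-test would remain a problem.

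What stands: the task analysis uses only participants with both visits, ignores a precision gain available from data already collected, and leaves missing post-tests and extreme scores without a rule.

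**Conclusion.** The point holds as a choice of a less efficient analysis, and it should be changed. It does not invalidate the trial. The firm part is precision: about 35%, 25% or 15% lower variance of the group effect at r = 0.3, 0.5 or 0.7, whatever the loss. This rests on an assumed correlation, since the plan gives none, and on equal variances at the two visits. The gain from retaining incomplete participants alone is small: 9.5%, 6.8% or 4.1% at the ceiling, and about 1% to 3% at r = 0.5 if 33 to 35 of 37 per arm complete. The protection against bias is real in kind but unknown in size; 0.10 SD at r = 0.5 is an illustration at the ceiling loss, not an estimate. The ±3 SD matter is secondary: a rule is missing, and it becomes outcome-based exclusion only if the scores are in fact removed.

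**What to change.** 1. Analyse each task outcome in all randomised participants by assigned group, with a mixed model: visit as a factor, group effect at post-test, unstructured covariance and a common baseline mean. When data are complete this is equivalent to post-test adjusted for baseline. State that it differs from the random-intercept model used for the scales.
2. State the analysis population and how many participants per arm lack a post-test for each task.
3. State what is done with participant-level indices beyond ±3 SD. Keep them in the main analysis. Show exclusion or winsorising, with the SD pooled over the arms, only as a sensitivity analysis.

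Cost: revised wording and a little more analysis; no new data. The statistical section is in the past tense and reports the outcome of the Levene test, so outcome data may already have been examined. If so, the change of model must be reported as made after that point, with the ANOVA results shown beside the new ones.

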However, most intervention studies just applied online tDCS stimulation to modify cognitive bias while overlooking its offline effects. Compared to short-term online effects, long-term offline effects are crucial for reducing intervention dependence and restoring normal social functioning. Moreover, previous studies have lacked direct tDCS interventions targeting socially anxious youth, resulting in insufficient consideration of the core characteristics and specific cognitive processing patterns associated with social anxiety. Specifically, regarding attention bias, prior studies have primarily focused on attentional vigilance while neglecting attentional avoidance (Jafari et al., 2021; Nejati & Estaji, 2024), a key characteristic of youth with social anxiety (Morales et al., 2015). In terms of interpretation bias, previous studies have failed to incorporate social contexts that may trigger negative evaluations into their measurement paradigms (Nejati et al., 2021), making it difficult to generalize findings from other clinical populations to socially anxious youth. Regarding memory bias, individuals with social anxiety tend to focus on their own performance in social situations, making them more likely to encode and retrieve self-referential negative memories. Thus, it is essential to examine tDCS effects on negative memory bias within a self-referential encoding framework. To address these gaps, the present study implemented offline tDCS stimulation and adjusted the stimulation protocol to enhance sustained intervention effects, and adopted a group-specific assessment paradigm to improve the precision of cognitive bias evaluation in socially anxious youth. In addition, while many studies have examined the effects of tDCS on attention, interpretation or memory bias individually (Jafari et al., 2021; Nejati & Estaji, 2024; Sanchez-Lopez et al., 2018; Winker et al., 2019), its influence on psychopathology symptoms remains underexplored. Given this, the current study utilized HD-tDCS as an intervention to explore changes in social anxiety symptoms.

In current study, we adopted a comparative intervention study with randomized controlled in which we delivered multiple courses of offline anodal HD-tDCS over the left DLPFC. The aim of this study was to explore the offline impact of HD-tDCS on cognitive bias (including attention, interpretation and memory bias) among youth with

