social anxiety symptoms. In addition, the researchers sought to further investigate the impact of tDCS stimulation on social anxiety. We hypothesized that anodal tDCS would activate the left DLPFC to facilitate cognitive control of threat-related information among youth with social anxiety, thereby reducing threat attention, interpretation and memory bias, and even improving social anxiety symptoms.

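### Ten or more task outcomes are tested at an unadjusted p<0.05, with a p<0.1 marginal tier and no rule for what supports the hypothesis

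*Combined protocol and SAP*

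**What the plan says.** All references are to the combined protocol and SAP.

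- **Analysis.** Data preparation and statistical analysis specifies group-by-time repeated-measures ANOVA (pre-test and post-test): "The outcomes of dot probe task, word sentence association paradigm and free recall and recognition task served as dependent variables". Significance is p<0.05, "and the marginal significance level was set at" p<0.1. Both levels cover all analyses, including the mixed models for the questionnaires. No adjustment is mentioned.
- **Dot probe task.** Four trial-level bias scores (mean and peak, positive and negative) are the main outcomes of that task. Angry faces are also classed as high or low intensity.
- **Word sentence association paradigm.** The threat and benign endorsement percentages are primary for interpretation bias. Two response-time indices are also calculated.
- **Free recall and recognition task.** There are four accuracies (positive and negative words, recall and recognition), none ranked. Words are encoded under three conditions.
- **Aim and hypothesis (Literature review).** "The aim of this study was to explore the offline impact of HD-tDCS on cognitive bias"; in addition, "the researchers sought to further investigate the impact of tDCS stimulation on social anxiety". The hypothesis is directional: stimulation would improve cognitive control, "thereby reducing threat attention, interpretation and memory bias, and even improving social anxiety symptoms".
- **Sample Size Calculation.** One repeated-measures ANOVA, effect size 0.25, alpha 0.05, power 0.95: 27 per group, raised to 37 for loss.

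**The concern.** The outcomes are defined task by task, but the final set of tests is not itemised. It is not stated whether the response-time indices count, or whether bias scores are split by face intensity or memory by encoding condition. The last gap matters because the Literature review says that "it is essential to examine tDCS effects on negative memory bias within a self-referential encoding framework", while the analysis section has no encoding factor.

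Nothing ranks one task above another, and nothing says which results, or how many, would support the hypothesis. An author with one favourable result among ten could claim support; a strict reader could require a result in all three domains. The plan allows both readings, and they carry very different chances of a false claim. The p<0.1 tier adds a second label with no instruction on how to interpret it.

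**Working it through.** **1. Count of outcomes.** Dot probe 4 + word-sentence endorsement 2 + memory 4 = 10. The two response-time indices make 12. Splits and questionnaires are left out.

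**2. The plan's own sample size.** Group-by-time interaction with two groups and m = 2 measurements: noncentral F(1, N−2) with λ = f²·N·m/(1−ρ). Inputs from the plan: f = 0.25 (the effect size read as Cohen's f) and alpha 0.05. The within-person correlation ρ is not given. With ρ = 0.5 assumed and N = 54, λ = 0.0625 × 54 × 2/0.5 = 13.5 and power is 0.950. This reproduces 27 per group. The calculation is for one test. At N = 74 with no loss, power is 0.989.

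**3. If any one favourable p<0.05 result of ten counts.** Under a global null, each two-sided test has a 0.025 chance of a result favouring tDCS.

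- Independent outcomes: 1 − 0.975^10 = 0.224. For twelve, 1 − 0.975^12 = 0.262.
- Common correlation r after turning each outcome to its favourable direction: 1 − ∫φ(u)·Φ((1.96 − √r·u)/√(1−r))^10 du. This gives 0.144 at r = 0.5 and 0.064 at r = 0.9.
- The 0.9 case is not a realistic lower end. Favourable here means less threat endorsement and more benign endorsement, and fewer negative but more positive words remembered. If the raw scores rise together (general memory ability, a habit of answering relevant), the benign and two positive-word outcomes correlate negatively with the others once oriented. With those three signs reversed, tasks independent and raw within-task correlation 0.5 / 0.7 / 0.9, the chance is 0.20 / 0.19 / 0.16.
- The plan does not state that more benign endorsement or better positive-word memory is favourable. With only the seven threat or negative-material outcomes, the independent figure is 1 − 0.975^7 = 0.162.

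**4. If at least one favourable result is needed in each task (4, 2, 4).**

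- Independent: (1 − 0.975^4)² × (1 − 0.975²) = 0.0963² × 0.0494 = 0.00046.
- Common correlation 0.5 / 0.7 / 0.9: 0.012 / 0.019 / 0.025.

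**5. If a marginal result were also read as support.** Any one of ten, independent: 1 − 0.95^10 = 0.401.

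**6. Power under Holm within each task** (same model, ρ = 0.5; the strictest step is the worst case of a step-down procedure).

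| Test level | 27 per group | 37 per group, no loss |
|---|---|---|
| 0.05 (as planned) | 0.950 | 0.989 |
| 0.025 (two outcomes) | 0.910 | 0.976 |
| 0.0125 (four outcomes) | 0.857 | 0.956 |

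Error is then controlled per task. Across three independent tasks, the chance of at least one false rejection in either direction is up to 1 − 0.95³ = 0.143.

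**The case against.** **The study is exploratory.** The aim uses that word, and so does the analysis section: "To explore the intervention effect of tDCS on task performance". This has weight, and an openly exploratory report would need no correction. But the same document states a directional hypothesis and powers the trial at alpha 0.05, and it never says that the task results are hypothesis-generating only.

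**The hypothesis is conjunctive.** It names attention, interpretation and memory bias together. If support requires all three, the null chance does not exceed that of a single test. This stands, and is why the 22% figure cannot be quoted alone. But the requirement is only implied by the wording; no decision rule states it.

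**Stronger readings that the documents do not support.** A reader might infer that:

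- *the plan has a 22% false-positive rate.* It does not: that figure needs an any-one rule that the plan never states, and independence.
- *the tests are unspecified.* The outcomes are defined in each task section; what is missing is the itemised final set and a ranking across tasks.
- *a p<0.1 result is to count as confirmation.* The plan defines the label but says nothing of that kind.
- *outcomes were chosen after seeing the results.* The analysis section does report a variance check in the past tense ("the results showed that the data basically satisfied the homogeneity of variance hypothesis"), so some data had been examined. It does not show that treatment effects had been seen or used to select outcomes.

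**Conclusion.** The concern holds as an omission that should be fixed. At least ten headline task outcomes are tested at an unadjusted p<0.05, with a p<0.1 tier, and there is no overall primary outcome, multiplicity control or support rule. Depending on the unstated rule, the null chance of apparent support runs from 0.05% to 2.5% (one result in each task) up to 22% (any one of ten, independent), against 2.5% for one test. Under the any-one rule it is 14% at an assumed common correlation of 0.5, and about 16% to 20% if the benign and positive-word outcomes run against the others and tasks are independent.

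The plan gives no correlations, so every correlated figure is an assumption, and all the percentages illustrate assumed rules. The omission itself depends on none of them.

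**What to change.** 1. In Data preparation and statistical analysis, apply Holm within each task to the outcomes already defined: four bias scores, two endorsement percentages, four memory accuracies. State that error is controlled per task only, with the 14% bound above.
2. Delete the p<0.1 tier. Report estimates, confidence intervals and exact p-values.
3. State that support for the full cognitive-bias hypothesis needs an adjusted favourable result in each of the three tasks, and that a result in one task supports that domain only. Define the favourable direction of each outcome.
4. Report the response-time indices and any face-intensity split as exploratory. Say whether memory is tested by encoding condition; if so, include those tests in the memory family.
5. Report the LSAS as the symptom outcome, and the NCPBQ subscales and STAI-T as supportive, not as further routes to a positive conclusion.
6. Label as post hoc any choice made after data were examined by group. If no correction is adopted, report all task results as exploratory.

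**Cost.** This changes wording and analysis only and needs no extra recruitment. At the assumed correlation of 0.5, power at the strictest step falls from 0.95 to 0.86 (four outcomes) or 0.91 (two) at 27 per group, and from 0.99 to 0.96 or 0.98 at 37 with no loss. Testing memory by encoding condition would enlarge that family and cost more. Holm across all ten would give control over all tasks together, but its strictest step (0.05/10 = 0.005) has power 0.77 at 27 and 0.92 at 37 per group. That makes it the more debatable choice.
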